#### 11.4.8 Discontinuation of Panitumumab

Panitumumab will be administered until subjects develop disease progression or are unable to tolerate panitumumab.

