## 4.0 OVERVIEW OF STUDY DESIGN/INTERVENTION

### 4.1 Design

A total of 78 patients whose liver metastases have been completely resected will be randomized 1:1 to two arms: patients in Arm A will receive Panitumumab in addition to HAI FUDR/Dexamethasone plus systemic CPT-11/5FU/LV, and patients randomized to Arm B will receive HAI FUDR/Dex plus systemic CPT-11/5FU/LV alone. Patients in both arms will be treated for a total of 6 cycles (7.5 months).

Cycle Schema q5 weeks			
Day 1	Day 15	Day 29	Day 36 (Day 1 of next cycle)
Pump Therapy FUDR* + Dexamethasone (14 day infusion)	Systemic ** +/- Panitumumab*** Pump Emptied Saline†	Systemic ** +/- Panitumumab*** Pump Emptied Saline	Pump Therapy FUDR + Dexamethasone (14 day infusion)

\*The following pump dose will be used:

FUDR 0.12 mg/kg \* kg \* 30 / pump flow rate

Dexamethasone flat dose of 25 mg

\*\* The following systemic doses will be used (at PI's discretion, lower dose of CPT-11 (150 mg/m^2) can be used if clinically appropriate and can be escalated to 150 mg/m^2):

CPT-11 150 mg/m^2 IV over 30 min to an hour

5FU 1000 mg/m^2/day cont. infusion over two days (no bolus FU)

Leucovorin 400 mg/m^2 IV over 30 min to an hour

\*\*\*For patients randomized to receive Panitumumab, the dose will be: **6 mg/kg IV, over 60 minutes**. Panitumumab will be given on Days 15 and 29 only.

‡ If clinically appropriate, patients will have pump emptied and filled with glycerol instead of heparin saline. Glycerol will last for 6 to 8 weeks; within that time, patient does not have to have pump filled with heparin and saline. If patients are allergic to heparin, they will receive Fondaparinux in the pump instead along with saline.

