#### **4.2 Intervention**

- All patients receive HAI FUDR (0.12 mg/kg/day X kg X pump volume) / pump flow rate and Dexamethasone flat dose of 25 mg on days 1.
- All patients receive CPT-11 (150 mg/m^2 IV over 30 min to an hour), Leucovorin (400 mg/m^2 IV over 30 min to an hour) and 5FU (1000 mg/m^2/day continuous infusion over two days) on days 15 and 29
- Randomization to panitumumab 6 mg/kg day 15 and 29 (or no panitumumab)
- Each cycle repeats every 36 days for a total of 6 cycles
- CT C/A/P every 2 cycles during treatment

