## 9.0 TREATMENT/INTERVENTION PLAN

9.1 Chemotherapy will be administered on a 5-week cycle basis. Pump therapy with FUDR and Dex will be administered on Day 1 of each cycle. The pump will be emptied and filled with heparin and normal saline on Days 15 and 29. Systemic chemotherapy will be administered on Days 15 and Day 29 of each cycle. Treatment recycles on Day 36.

On Days 15 and 29, patients will receive systemic chemotherapy. Patients on the panitumumab arm will receive the drug over a 60 minute infusion first. CPT-11/LV will be administered subsequently via a Y-line over a 30 to 60 minute infusion, and 5FU will follow by a 48-hour infusion.

9.2 For the first cycle, the dose of FUDR will be calculated based on the predetermined flow rate provided by the pump manufacturer. Thereafter, doses will be adjusted (lowered, if necessary, but never increased) based on actual observed flow rate. The pump will be filled with FUDR, Dexamethasone, heparin and saline.

Dose calculation:

FUDR:  $\frac{0.12 \text{ mg/kg} \times \text{kg (patient weight)} \times \text{pump volume}}{\text{pump flow rate}}$

Dexamethasone: flat dose of 25 mg

*Overweight patients:*

If a patient is 35% above ideal weight, dose of FUDR chemotherapy will be calculated as follows:

To calculate Ideal Body weight (kg):

Males:  $50\text{kg} + (2.3 \times \text{height in inches above 5 ft})$   
(i.e.: for a patient who is 5'10", use 10)

Females:  $45.5\text{ kg} + (2.3 \times \text{height in inches above 5 ft})$

*Example:* An overweight male is 106 kg and 5'11"

$50\text{kg} + (2.3 \times 11) = 50\text{kg} + 25.3 = 75.3$  is the Ideal Body Weight

To calculate Ideal Average weight (kg):

Actual weight + Ideal Body Weight

2

*Using the male example from above:*

$106 + 75.3 = 181.3 \div 2 = 90.65$  is the Ideal Average Weight

Use the Ideal Average Weight to calculate the FUDR dose in patients who are overweight\*.

\* If PI feels the patient is an appropriate weight, the ideal average weight equation should not be used and patients can have the regular dose calculation of FUDR.

Heparin: 30,000 units total dose

Normal saline: quantity sufficient to make total reservoir volume of 30 ml.

If no dose modification due to toxicity is required, the dosages given above (adjusted for changes in weight and pump flow rate) will be repeated on Day 1 of Cycle 2 and all subsequent cycles.

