- If patients return for FUDR and the liver function tests (SGOT, alkaline phosphatase and/or bilirubin) are too elevated (as in table 1) patients will wait one to two weeks. If they are still elevated, patients will start the next cycle with systemic and not with FUDR. During that cycle if the liver function tests come down enough (according to Table Recommencing Treatment After Hold), patients will be able to receive FUDR again at a lower dose. In that case they can receive the FUDR, then two weeks later they will receive systemic once afterwards and then move onto the next cycle.
- If liver function tests are too high for a patient to receive FUDR, they may continue on study treatment with systemic chemotherapy for a total of 12 systemic treatments. In this case, the patient will be treated with systemic treatment on Day 1 and on Day 15, then move onto the next cycle starting with Day 1.

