- Subjects treated at the 60% dose level whose toxicity does not recur should receive the 80% dose at the next dose unless a previous attempt to re-escalate to the 80% dose level was not tolerated (re-initiation of the 60% dose is allowed as an alternative to dose escalation).

- Subjects who miss more than 2 consecutive scheduled doses due to toxicity or are unable to receive a dose of panitumumab within 6 weeks of having received their previous dose of panitumumab due to toxicity will be considered unable to tolerate panitumumab and will not be retreated with panitumumab.
- If a subject demonstrates a clinical benefit with a documented response of stable disease, partial response or complete response and there are reasons that the dose modification rules above cannot be implemented, the investigator should contact and discuss these reasons with Amgen. The investigator must obtain written agreement from Amgen before any changes in the dose modification rules can be implemented.

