## 12.0 CRITERIA FOR THERAPEUTIC RESPONSE/OUTCOME ASSESSMENT

- 12.1 Assessments of tumor response to treatment while on treatment are not appropriate since tumor is resected.
- 12.2 Patients will receive 3 CT scans of the chest, abdomen and pelvis during treatment (every 2 cycles). Scans will be assessed closely for disease status and possible recurrence. Our definition of recurrence will be any lesion growing in the liver or extrahepatic sites that is felt by the reference radiologist to be new disease.
- 12.3 CT scan of the chest, abdomen and pelvis and CEA every 12 weeks for the first 2 years after the completion of treatment. A CT scan will coincide with 15 months after treatment start, which will allow us to determine 15 month RFS.

Baseline CT scan	0 weeks
CT # 2	10 weeks after treatment start
CT # 3	20 weeks
CT # 4	30 weeks
End treatment	
CT # 5	42 weeks
CT # 6	54 weeks
CT # 7	66 weeks (+/- 3 weeks)

- 12.3 Colonoscopy within the first 2 years after completion of treatment; this test will enable us to determine whether the patients are NED.
- 12.4 CT scan of the chest, abdomen and pelvis and CEA every 4 months between 2 and 4 years after completion of the treatment. CT scan of the chest, abdomen and pelvis and CEA every 6 months for five years, and yearly thereafter until patient expires. The follow-up scans are necessary to determine the RFS of this patient population.

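### Section 11.4.8 continues panitumumab until progression or intolerance with no cycle limit, while Sections 1.0, 4.1 and 4.2 fix treatment at 6 cycles, and nothing reconciles the two

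*Combined protocol and SAP*

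**What the plan says.** The protocol describes the duration of panitumumab in two ways.

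**A fixed course.**
- Section 4.1: "Patients in both arms will be treated for a total of 6 cycles (7.5 months").
- Section 4.2, and Section 1.0 in the same terms: "Each cycle repeats every 36 days for a total of 6 cycles".
- Within a cycle, Section 4.1 says: "Panitumumab will be given on Days 15 and 29 only".
- Section 9.1: "Chemotherapy will be administered on a 5-week cycle basis".
- Section 11.4.2, in the text on restarting after a hold, says of patients whose liver tests rule out FUDR: "they may continue on study treatment with systemic chemotherapy for a total of 12 systemic treatments".
- Section 12.2 plans three on-treatment scans, one every two cycles. The schedule in Section 12.3 places the end of treatment after the week-30 scan.

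**A course with no stated end.**
- Section 11.4.8: "Panitumumab will be administered until subjects develop disease progression or are unable to tolerate panitumumab".

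Two related statements also do not fit together. The last bullet of Section 11.4.6 opens an exception to the dose-modification rules with "If a subject demonstrates a clinical benefit with a documented response of stable disease, partial response or complete response". Section 12.1 says: "Assessments of tumor response to treatment while on treatment are not appropriate since tumor is resected".

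The primary endpoint is 15-month recurrence-free survival (RFS). Section 12.3 times the deciding scan from treatment start. Section 14.0 judges each arm by whether at least 24 of 39 patients are alive and disease free at that point, and declares a winner on a lead of at least 3.

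**The concern.** Panitumumab is the only randomised component, so its duration defines the intervention being tested. Take a patient in Arm A (panitumumab) who reaches week 30 without recurrence and without intolerance. Under Section 4.1 this patient has finished treatment. Under Section 11.4.8 neither stopping condition has been met. The protocol gives both instructions and does not say which prevails.

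Only Arm A receives the drug, so an open-ended rule would affect one arm only. At 15 months the trial would then compare patients still on panitumumab with patients some 8 months off all treatment. A higher RFS in Arm A could reflect continued dosing rather than the addition of panitumumab to the 6-cycle regimen, which is the question Section 1.0 sets out. If treating physicians resolved the conflict differently, Arm A would mix two regimens, and its count against the threshold of 24 would belong to neither.

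**Working it through.** **1. The plan's own design figures.** Inputs from Section 14.0: 39 per arm, threshold 24, rates of 50% and 70%, winning lead 3.
- Type I error: P(X ≥ 24 | n = 39, p = 0.5) = 0.0998 (stated 10%).
- Power: P(X ≥ 24 | n = 39, p = 0.7) = 0.9056 (stated type II error 10%).
- Enumerating two independent binomial arms at 70% and 50%: better arm selected 84.6%, none selected 8.5%, tie 6.2%, worse arm selected 0.7% (stated 85%, about 9% and 6%).

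These reproduce. Duration of treatment enters none of them, so the conflict does not disturb the sample size or the error rates.

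**2. Length of the fixed course.**
- With a 5-week cycle (Section 9.1): 6 × 35 = 210 days = 30 weeks. This matches the end-of-treatment line in Section 12.3, and is 7.5 four-week months (210 ÷ 28) as in Section 4.1.
- With a 36-day repeat (Sections 1.0 and 4.2): 6 × 36 = 216 days = 30.9 weeks.

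**3. Time from the end of the course to the endpoint.**
- 15 months = 15 × 30.44 = about 457 days = 65.2 weeks (scan 7 is set at week 66).
- 457 − 210 = 247 days, or about 35 weeks (8.1 months).
- 247 ÷ 457 = 54% of the period up to the endpoint.

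**4. Doses under each reading.**
- Fixed course: 6 cycles × 2 doses = 12. With 35-day cycles the last falls on day 5 × 35 + 29 = 204.
- No cycle limit, 35-day cycle: 457 ÷ 35 = 13.05, so 13 complete cycles and 13 × 2 = 26 doses.
- No cycle limit, 36-day cycle: 12 complete cycles end at day 432. One further Day 15 dose falls before day 457 and the next Day 29 dose falls after it, giving 12 × 2 + 1 = 25.

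The figures of 25 and 26 are upper bounds. They assume that the Day 15 and Day 29 pattern continues after cycle 6, that no dose is missed, and that progression in Section 11.4.8 means recurrence in this resected population.

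**5. Whether another section settles it.**
- Section 9.2 repeats dosing in cycle 2 and later cycles without giving a total.
- Section 13.0 does not list completing 6 cycles as a reason for coming off treatment.
- The limit of 12 in Section 11.4.2 concerns systemic chemotherapy when FUDR cannot be given, and does not name panitumumab.
- Section 11.4.8 refers to none of these.

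The 6-cycle limit on panitumumab therefore has to be inferred from Sections 1.0, 4.1, 4.2 and 12, against the literal wording of 11.4.8.

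**The case against.** The best reply is that the fixed course is stated plainly and more than once. Section 4.1 applies it to both arms, the scan plan is built on it, and panitumumab days are defined only within a cycle. Section 11.4.8 sits under dose modifications in the toxicity chapter, so it can be read as listing reasons to stop early within the 6 cycles. That is a fair reading and most of the protocol supports it. The two durations are not equally supported. What remains is that 11.4.8 does not limit itself in this way, and a reader must supply the limit.

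A reader might also infer more than the documents support:
- **That 11.4.8 is the only rule for stopping panitumumab.** Section 11.4.6 (toxicity at the 60% level, missed doses), Section 11.4.11 (proscribed therapy, unexpected surgery) and Section 13.0 also stop it. None of them sets a planned duration.
- **That sites would differ.** Section 15 recruits and registers patients through one centre. The allowance for local oncologists in Section 10.1 covers Arm B only, and Section 5.6.1 restricts panitumumab to this trial's investigators. Differences between treating physicians are possible; a between-site mechanism is not in the documents.
- **That the endpoint scan would move.** The table in Section 12.3 fixes scans through week 66 from treatment start. Only the later follow-up, worded from completion of treatment, would lose its starting point.
- **That the response wording in 11.4.6 sets duration or has to be removed.** It concerns departures from dose-modification rules with the drug supplier's agreement. It conflicts with Section 12.1, and the two need reconciling; the documents support no more than that.

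**Conclusion.** The contradiction is real and should be resolved, because it concerns the duration of the only randomised drug. Followed literally, Section 11.4.8 allows panitumumab in Arm A for about 35 of the 65 weeks up to the primary endpoint, when Sections 1.0, 4.1, 4.2 and 12 have both arms off treatment. In doses, that is 12 against at most 25 to 26, on the stated assumption of an unchanged schedule after cycle 6. The effect is on what the 24-of-39 rule and the 3-patient margin would be judging. The design's operating characteristics and the timing of the 15-month assessment are unaffected.

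A reader might conclude that the trial was planned as open-ended maintenance in one arm, or that Arm A patients will receive about twice the planned doses. The documents do not support either as fact. They show a stated rule that permits this, a larger body of text pointing to a fixed course, and nothing that says which governs.

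**What to change.** Reconcile Section 11.4.8 with Sections 1.0, 4.1 and 4.2, the limit of 12 systemic treatments in Section 11.4.2, and the end-of-treatment line in Section 12.3. One panitumumab duration should apply to every Arm A patient, and the primary objective should describe that regimen. Section 11.4.8 should state how it relates to the 6 cycles and cross-refer to the section that governs. Separately, reconcile the response-based wording in Section 11.4.6 with Section 12.1. Which duration applies is for the sponsor to decide.

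The cost is protocol wording only. No patients or procedures are added, and the design in Section 14.0 does not need recalculating.

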#### 11.4.9 Guidelines for Diarrhea Management

- Symptoms of diarrhea and/or abdominal cramping may occur at any time and should be managed according to standard institutional practice.
- Subjects should also be instructed to notify the investigator or nurse for the occurrence of bloody or black stools, symptoms of dehydration, fever, inability to take liquids by mouth, inability to control diarrhea (return to baseline) within 24 hours. Subjects with diarrhea should be evaluated frequently by a nurse or physician until resolution of diarrhea.
- Changes in electrolytes, even without BUN/urea and/or creatinine elevation, may reflect early physiologic consequences of treatment-induced gastrointestinal toxicity. Subjects with clinically significant electrolyte changes should be evaluated for dehydration and receive aggressive fluid and electrolyte replacement, if indicated.

#### 11.4.10 Electrolyte Management

- Subjects should be evaluated as outlined in Section 11 and managed as per local medical practice. If hypomagnesemia is present, replacement should be managed with either oral or parenteral replacement, or both, according to institutional practice and to the degree of hypomagnesemia present. It is recommended that subject's serum magnesium level should be maintained within the normal range during study treatment.
- It is important to assess and manage serum potassium and calcium (adjusted for albumin) in subjects who have concomitant hypomagnesemia. Subject's serum potassium and calcium parameters are recommended to be maintained, as per local medical practice, within the normal ranges during study treatment.

#### 11.4.11 Proscribed Therapy During Study Period

- Subjects must be withdrawn from the study if they receive any other investigational agents, anti-EGFr targeting agents other than panitumumab, experimental or approved anti-tumor therapies (e.g., bevacizumab), chemotherapy or radiotherapy (with the exception of use for pain control).

- Subjects should not schedule any elective surgeries (excluding central venous catheter placement) during their participation in the study, or until 7 days after their last administration of study treatment. If a subject undergoes any unexpected surgery during the course of the study, that subject must discontinue all study treatment immediately, and the sponsor should be notified as soon as possible. A subject may be allowed to resume study treatment after each surgical case is reviewed by the sponsor study team in conjunction with the investigator to determine the appropriateness of treatment resumption.
- Patients will be prophylactically administered minocycline and a topical steroid. If toxicity cannot be managed, [name] will see the patients for evaluation.

## 12.0 CRITERIA FOR THERAPEUTIC RESPONSE/OUTCOME ASSESSMENT

- 12.1 Assessments of tumor response to treatment while on treatment are not appropriate since tumor is resected.
- 12.2 Patients will receive 3 CT scans of the chest, abdomen and pelvis during treatment (every 2 cycles). Scans will be assessed closely for disease status and possible recurrence. Our definition of recurrence will be any lesion growing in the liver or extrahepatic sites that is felt by the reference radiologist to be new disease.
- 12.3 CT scan of the chest, abdomen and pelvis and CEA every 12 weeks for the first 2 years after the completion of treatment. A CT scan will coincide with 15 months after treatment start, which will allow us to determine 15 month RFS.

Baseline CT scan	0 weeks
CT # 2	10 weeks after treatment start
CT # 3	20 weeks
CT # 4	30 weeks
End treatment	
CT # 5	42 weeks
CT # 6	54 weeks
CT # 7	66 weeks (+/- 3 weeks)

- 12.3 Colonoscopy within the first 2 years after completion of treatment; this test will enable us to determine whether the patients are NED.
- 12.4 CT scan of the chest, abdomen and pelvis and CEA every 4 months between 2 and 4 years after completion of the treatment. CT scan of the chest, abdomen and pelvis and CEA every 6 months for five years, and yearly thereafter until patient expires. The follow-up scans are necessary to determine the RFS of this patient population.

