### Therapeutic Intervention

- All patients receive HAI FUDR (0.12 mg/kg/day X kg X pump volume) / pump flow rate and Dexamethasone flat dose of 25 mg on days 1.
- All patients receive CPT-11 (150 mg/m^2 IV over 30 min to an hour), Leucovorin (400 mg/m^2 IV over 30 min to an hour) and 5FU (1000 mg/m^2/day continuous infusion over two days) on days 15 and 29
- Randomization to panitumumab 6 mg/kg day 15 and 29 (or no panitumumab)
- Each cycle repeats every 36 days for a total of 6 cycles.

This phase II study aims to assess the efficacy of panitumumab with HAI in combination with systemic chemotherapy in patients with completely resected hepatic metastases from colorectal cancer. The protocol includes biological correlative studies. The primary objective of this study is to determine if the RFS increases with the addition of concurrent intravenous Panitumumab to HAI plus systemic chemotherapy after hepatic resection. This study will 1:1 randomize 78 patients who are all-RAS wild type after liver resection to HAI FUDR and dexamethasone with systemic chemotherapy, +/- systemic Panitumumab. The primary endpoint is 15 month RFS.

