## 10.0 EVALUATION DURING TREATMENT/INTERVENTION

	Day 1* each cycle	Days of systemic chemotherapy**	Q10 weeks approximately after treatment start
HX, PE, MD or NP visit	X		
HX, Nurse visit		X	
Tox assessment	X		
Weight	X		
KPS	X		
CBC, Plts	X	X	
BUN, Creat	X	X	
Bili, SGOT, SGPT	X	X	
Alk phos, LDH	X	X	
Electrolytes	X	X	
CEA	X	X	
Magnesium (for patients randomized to Panitumumab arm)	X	X	
Calcium	X	X	
CT Chest/abdomen/pelvis***			X

\* Or within 48 hours prior to Day 1

\* Or within 72 hours prior to Day 15 and Day 29

\*\*\* MRI may be obtained instead of CT if patient's disease is not visible on CT. Allowances of +/-3 weeks will be acceptable.

10.1 While being treated with protocol therapy, patients will be seen at or prior to the first day of each cycle by their medical oncologist.

In cases approved by the Principal Investigator, patients randomized to Arm B (no panitumumab) can see local oncologists for systemic treatments.

10.2 Patients will be assessed for adverse events prior to administration of systemic chemotherapy, panitumumab, or HAI.

10.3 Patients will have an end of study assessment for toxicity.

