### **11.2 Toxicity Related to Panitumumab**

Toxicities will be recorded as adverse events on the Adverse Event case report form and must be graded using The National Cancer Institute's Common Toxicity Criteria (CTC) version 4.0.

Dermatologic Toxicity: Dermatologic toxicities occurred in 89% of patients and were severe (NCI-CTC grade 3 and higher) in 12% of patients receiving Panitumumab monotherapy. The clinical symptoms include, but are not limited to, dermatitis acneiform, pruritus, erythema, rash, skin exfoliation, paronychia, dry skin, and skin fissures. In some cases, it may cause infected sores requiring medical and/or surgical treatment, or cause severe skin infections that could be fatal. Subsequent to the development of severe dermatologic toxicities, infectious complications, including sepsis, septic death, and abscesses requiring incisions and drainage were reported.

Infusion Reactions: Severe infusion reactions included anaphylactic reactions, bronchospasm, and hypotension, which occurred in approximately 1% of patients.

Pulmonary fibrosis: In patients enrolled in clinical studies of Panitumumab, pulmonary fibrosis occurred in less than 1% (2/1467). Patients with a history of interstitial pneumonitis, pulmonary fibrosis, evidence of interstitial pneumonitis, or pulmonary fibrosis were excluded from clinical studies. Therefore, the probability of risk in a general population is uncertain.

**Electrolyte Depletion/Monitoring:** In patients enrolled in a clinical trial, 2% experienced hypomagnesemia (NCI-CTC grade 3 or 4), which required oral or IV electrolyte repletion. Hypomagnesemia occurred 6 weeks or longer after the initiation of Panitumumab. In some patients, both hypomagnesemia and hypocalcemia occurred.

**Photosensitivity:** Exposure to sunlight can worsen dermatologic toxicity. It is recommended that patients wear sunscreen and hats and limit sun exposure while receiving Panitumumab.

**Dermatologic, Mucosal, and Ocular Toxicity:** Ocular toxicities occurred in 15% of patients and included, but were not limited to: conjunctivitis (4%), ocular hyperemia (3%), increased lacrimation (2%), and eye/eyelid irritation (1%). Stomatitis (7%) and oral mucositis (6%) were reported. One patient experienced an NCI-CTC grade 3 event of mucosal inflammation. The incidence of paronychia was 25% and was severe in 2% of patients. Nail disorders were observed in 9% of patients.

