## 13.0 CRITERIA FOR REMOVAL FROM STUDY

- 13.1 Development of clear-cut evidence of recurrent colorectal cancer in the liver compared to the baseline postoperative CT scan, via clinical exam or imaging studies. These patients will still be followed for recurrence and survival.

- 13.2 Development of clear-cut evidence of extrahepatic recurrence via clinical exam or imaging studies. These patients will still be followed for recurrence and survival.
- 13.3 Patient is unable to resume hepatic arterial FUDR due to hepatic toxicity. These patients will still be followed for recurrence and survival.
- 13.4 Unacceptable toxicity that does not respond to the dosage modification. Even if patients cannot tolerate treatment they will be continued to be followed for survival and recurrence.
- 13.5 Patient elects to discontinue treatment.
- 13.6 Changes in a patient's condition which render the patient unacceptable for further treatment in the judgment of the investigator. These patients will still be followed for recurrence and survival.

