#### **14.0 BIOSTATISTICS**

This study will 1:1 randomize 78 patients to two treatment arms: HAI FUDR and dexamethasone with systemic chemotherapy, +/- systemic Panitumumab. Randomization procedures will be discussed in section 15.2.

The primary endpoint is 15 month recurrence free survival (RFS). Based on an exact binomial single stage design, with 39 patients in each arm we are able to differentiate between unacceptable 15 month RFS of 50% and acceptable 15 month RFS of 70% with type I error (falsely accepting a non-promising therapy) and II error (falsely rejecting a promising therapy) rates of 10 % each. For a particular arm, if 24 or more patients are alive and disease free at 15 months the regimen in that arm will be considered worthy of further investigation. We will use the —pick the winner— format based on the randomized phase II clinical trials approach proposed by Simon et al. (1985) to differentiate between 15 month RFS of 50% and 70%. The pick the winner role only occurs if both regimens are efficacious. If the number of patients who are disease free and alive at 15 months in one arm is at least 24 and it exceeds by at least 3 patients the number of alive and disease free patients at 15 months in the other arm, then the arm with the higher 15 months RFS would be declared the winner. If neither arm had at least 24 patients alive and disease free at 15 months, the regimens in both arms would be considered unworthy of further evaluation. The probability of selecting the better regimen is 85%; the probability that no regimen is selected is approximately 9%, while the probability of a tie is 6 % (Simon R, Wittes RE, Ellenberg SS. (1985). Randomized phase II clinical trials. *Cancer Treat Rep* 69, 1375-1381.)

RFS will also be estimated using the Kaplan Meier method. As secondary endpoint, overall survival will be estimated by the Kaplan Meier method. Associations between biomarkers and RFS and overall survival will be assessed using the log-rank test. In each arm, safety and tolerability will be summarized using descriptive statistics.

The prevalence of RAS mutations is about 40%; therefore we would have to approach about 120 patients in order to accrue 78 patients. On average, we see about 40 eligible patients per year; therefore we would need three years to reach 120.

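### Nothing in the plan masks the reference radiologist to treatment arm, although that judgement supplies the recurrence part of 15-month RFS and a 3-patient lead can name the winner

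*Combined protocol and SAP*

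**What the plan says.** Section 12.2, repeating section 3.1.1, defines recurrence as "any lesion growing in the liver or extrahepatic sites that is felt by the reference radiologist to be new disease". Neither place gives a measurement or confirmation threshold, and neither says whether the radiologist knows the treatment arm. Section 13.0 uses a different standard for removal from study: "Development of clear-cut evidence of extrahepatic recurrence via clinical exam or imaging studies". It names no reference radiologist.

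Section 14.0 makes 15-month RFS the primary endpoint, counted as patients alive and disease free at 15 months. Each arm of 39 needs at least 24 such patients, and an arm wins if it reaches 24 and "it exceeds by at least 3 patients the number of alive and disease free patients at 15 months in the other arm".

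The trial is not labelled open in the text available. Openness follows from sections 1.0 and 4.1, where the comparator is the same regimen without panitumumab and no placebo is described. It also follows from section 10.1, where, with approval, "patients randomized to Arm B (no panitumumab) can see local oncologists for systemic treatments". Section 11.2 adds that on panitumumab monotherapy "Dermatologic toxicities occurred in 89% of patients", so treating staff will usually be able to tell the arm.

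**The concern.** The between-arm decision is a comparison of two raw counts, and one component of each count is a judgement. If the person making it knows the arm, equivocal findings after liver resection, or in lung or nodes, may be handled differently in the two arms without anyone intending it. The background text expects anti-EGFR treatment to help at lung and nodal sites, so a direction for such an influence is at least conceivable.

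Two decisions are exposed: the between-arm lead of 3, and each arm's own threshold of 24 of 39. Randomization does not protect against this, because the difference would arise after allocation, when the outcome is read.

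**Working it through.** **Inputs from section 14.0.** 39 patients per arm; unacceptable and acceptable 15-month RFS of 50% and 70%; threshold 24; lead of 3; stated error rates 10% each; stated selection probabilities 85% (better arm), about 9% (none) and 6% (tie).

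**Step 1: the plan's own figures.** With X ~ Binomial(39, p):
- type I error = P(X ≥ 24 | p = 0.50) = 0.0998
- power = P(X ≥ 24 | p = 0.70) = 0.9056, so type II error = 1 − 0.9056 = 0.094

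For two independent arms, P(A wins) = Σ P(X_A = i) P(X_B = j) over all i ≥ 24 with i − j ≥ 3. At 70% against 50% this gives 84.6% better arm selected, 8.5% none, 6.2% tie and 0.7% worse arm selected. The stated 85%, 9% and 6% are reproduced. If the lead were required only when both arms reach 24, the results would be 86.4%, 8.5% and 4.0%, a poorer match on ties, so the first form is used below.

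**Step 2: size of the lead.** 3/39 = 7.7 percentage points.

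**Step 3: hypothetical differential reading.** Assume equal true rates p. In one arm, k more patients of 39 (in expectation) are read as recurrence free than would be under even-handed reading. That arm's rate becomes p + k/39 and the other stays at p. For example, at p = 0.60 and k = 2 the rates are 0.60 + 0.0513 = 0.6513 and 0.60. The chance that the favoured arm is named winner is:

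| True RFS, both arms | k = 0 | k = 1 | k = 2 | k = 3 |
|---|---|---|---|---|
| 50% | 8.1% | 13.9% | 21.8% | 32.0% |
| 60% | 24.0% | 32.9% | 42.8% | 53.0% |
| 70% | 26.8% | 35.3% | 45.0% | 55.2% |

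**Step 4: the single-arm threshold.** At a true 50%, the chance that one arm reaches 24 goes from 10.0% to 16.8%, 26.1% and 37.6% for k = 1, 2 and 3.

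**Step 5: the opposite direction.** With true rates of 70% and 50%, and the better arm read too harshly by k/39, correct selection falls from 84.6% to 76.1%, 65.4% and 53.5% for k = 1, 2 and 3.

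The values of k are assumptions throughout. The documents supply none.

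**The case against.** The plan has real protections. A reference radiologist is designated, the lesion must be growing, there is a baseline CT, and both arms follow the same CT schedule to week 66 (± 3 weeks). The endpoint is also a landmark, so calling a lesion early or late matters only if it moves the patient across the 15-month assessment. A lesion seen well before then that keeps growing should be called in either arm. All of this stands, and it limits how many patients could be affected. It does not address the equivocal lesion near the landmark.

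Several stronger readings are tempting, and the documents do not support them:
- *The primary endpoint is whatever the radiologist feels.* The definition requires growth, and deaths count as failures too. Only the recurrence component involves this judgement.
- *The radiologist knows the arm, or will favour panitumumab.* The plan is silent on what the radiologist is told. Skin toxicity is visible to clinicians and is not shown to be visible on CT. No direction of bias is documented.
- *Two or three calls decide the winner.* They matter only when the counts already lie near the 3-patient lead or the threshold of 24. At 60% with a 2-patient shift, the favoured arm still fails to win 100 − 42.8 = 57.2% of the time.

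Reading error that is equal in both arms favours neither, and masking would not remove it. Finally, this is a 78-patient phase II selection trial, and omitting masking contradicts nothing else in the plan.

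**Conclusion.** The concern holds as a gap in how the endpoint is read; the statistical figures in section 14.0 reproduce. The recurrence component of 15-month RFS rests on a judgement by a radiologist whom the plan does not mask, in a trial that is open by inference, and it feeds a rule that needs a lead of only 3 patients.

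The sensitivity is material. A net shift of 2 of 39 patients adds 13.7 points (21.8 − 8.1), 18.8 points (42.8 − 24.0) or 18.2 points (45.0 − 26.8) to one arm's chance of winning at equal true RFS of 50%, 60% or 70%. The same shift against a truly better arm costs 19.2 points of correct selection (84.6 − 65.4).

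These figures show what would follow if such a shift occurred. They do not estimate its likelihood, and they assume independent binomial counts and a difference that depends on arm. The point is worth acting on because masking is inexpensive, without any claim that the result will be biased.

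**What to change.** In section 12.2, state that the existing reference radiologist makes the recurrence read used for 15-month RFS from imaging requests that omit the treatment arm, and that this single masked read is the endpoint source for both arms. This would also settle that the section 13.0 wording on removal from study does not supply the primary endpoint.

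Sample size, thresholds, scan schedule and treatment stay as they are. No extra radiologist is needed if the routine read is itself made from the arm-free request. The cost is minor administrative work to keep the arm off requests, and a radiologist who reads with less clinical context.
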